13.1.1.5. Investigator Global Aesthetic Improvement Scale (I-GAIS)

Investigators will complete the I-GAIS on subjects in the observation-only group as described below at the final study visit (month 12 or early termination) and a comparison back to the pre-treatment Day 1 (Baseline) image of the assigned quadrant of the double-blind study.

On Day 71 of the treatment course and the 12 month or end of study visit, the Investigator will determine the degree of improvement from the Screening B digital image of the selected quadrant by comparing the cellulite in live assessment on Day 71 and at month 12 or study end to the Screening B pre-treatment (Baseline) image of the subject's selected quadrant (Table 9). The I-GAIS assessment will occur after the CR-PCSS assessment (section [13.1.1.4](#)) to avoid introducing potential bias to the static CR-PCSS assessment by the Investigator at the site.

Table 9: Investigator Global Aesthetic Improvement Scale (I-GAIS)

Rating	Response Option	Description
+3	Very much improved	Optimal cosmetic result from treatment of the treated dimples
+2	Much improved	Marked improvement in the treated area appearance from before treatment, but not completely optimal
+1	Improved	Obvious improvement in the treated area appearance from before treatment, but additional treatment is indicated
0	No change	The treated area appearance is essentially the same as before treatment
-1	Worse	The treated area appearance is worse than before treatment
-2	Much worse	Marked worsening in appearance from the initial condition
-3	Very much worse	Obvious worsening in appearance from the initial condition

13.1.1.6. Hexsel Cellulite Severity Scale

The Hexsel Cellulite Severity Scale (referred to as the Hexsel CSS) is a photonumeric scale that looks at 5 key morphologic features of cellulite: (A) number of evident depressions, (B) depth of depressions, (C) morphological appearance of skin surface alterations, (D) laxity, flaccidity or sagging of skin, and (E) current classification scale based on medical literature including Nürnberg and Müller.([12,13](#)) Each of these features is evaluated on a 4-point scale from a low of 0 to a high of 3 as described in [Table 10](#) (see [Appendix B](#)). The total score is the summation of all 5 features.

For subjects in the observation-only group, the Hexsel CSS will be done at the month 12 or the end of study visit, and at months 15, 18, 21, and 24 for subjects originally treated with active EN3835 in the double-blind study that are being assessed for treatment durability beyond 1 year.

For the subjects electing treatment (re-treatment or re-dosing) with EN3835 the Investigator or qualified designee will independently use the Hexsel CSS to assess the severity of EFP in all quadrants at Screening B visit and the selected quadrant on Day 71 of the course of treatment and at month 12 or end of study visit. All cellulite assessments should be made while the subject is in the standing position with relaxed gluteus muscles. However, when evaluating the subject for Category E (classification scale by Nürnberg and Müller) ([13](#)) if the subject has no evident depressions, the subject should be asked to contract her gluteus muscles or the pinch test should

be applied (by pinching the skin between the thumb and index finger) so the Investigator or qualified designee can differentiate between scores/grades of zero (0) or I.

Table 10: Hexsel Cellulite Severity Scale

A	Number of evident depressions	0=none/no depressions 1=a small amount: 1-4 depressions are visible 2=a moderate amount: 5-9 depressions are visible 3=a large amount: 10 or more depressions are visible
B	Depth of depressions	0=no depressions 1=superficial depressions 2=medium depth depressions 3=deep depressions
C	Morphological appearance of skin surface alterations	0=no raised areas 1='orange peel' appearance 2='cottage cheese' appearance 3='mattress' appearance
D	Grade of laxity, flaccidity, or sagging skin	0=absence of laxity, flaccidity, or sagging skin 1=slight draped appearance 2=moderate draped appearance 3=severe draped appearance
E	Classification scale by Nürnberger and Müller ^a	0 = zero grade = Grade or Stage 0 = There is no alteration of the skin surface. 1 = first grade = Grade or Stage I = The skin of the affected area is smooth while the subject is standing or lying, but the alterations to the skin surface can be seen by pinching the skin or with muscle contraction. 2= second grade = Grade or Stage II = The orange skin or mattress appearance is evident when standing, without the use of any manipulation (skin pinching or muscle contraction). 3= third grade = Grade or Stage III = The alterations described in Grade or Stage II, are present together with raised areas and nodules.

Source: Hexsel DM, Dal’Forno T, Hexsel CL. A validated photonumeric cellulite severity scale. *J Eur Acad Dermatol Venereol.* 2009;23(5):523-528.

^a Subjects should be evaluated in the standing position with relaxed gluteus muscles. However, if the subject has no evident depressions, they should be asked to contract their gluteus muscles or the pinch test should be applied (by pinching the skin between the thumb and index finger) in order to differentiate between grade/stage of zero (0) or I.

14. ASSESSMENT OF SAFETY

14.1. Definitions

14.1.1. Adverse Event

An adverse event (AE) is any unfavorable or unintended change in body structure (signs), body function (symptoms), laboratory result (eg, chemistry, ECG, X-ray, etc), or worsening of a pre-existing condition associated temporally with the use of the study medication whether or not considered related to the study medication. AEs will be captured once a subject has signed the informed consent. AEs include:

- Changes in the general condition of the subject
- Subjective symptoms offered by or elicited from the subject
- Objective signs observed by the Investigator or other study personnel
- All concurrent diseases that occur after the start of the study, including any change in severity or frequency of pre-existing disease
- All clinically relevant laboratory abnormalities or physical findings that occur during the study

A treatment-emergent adverse event (TEAE) is any condition that was not present prior to treatment with study medication but appeared following treatment, was present at treatment initiation but worsened during treatment, or was present at treatment initiation but resolved and then reappeared while the individual was on treatment (regardless of the intensity of the AE when the treatment was initiated).

All AEs, including both observed or volunteered problems, complaints, signs or symptoms must be recorded on the AE page of the eCRF, regardless of whether associated with the use of study medication. This would include AEs resulting from concurrent illness, reactions to concurrent medication use, or progression of disease states (excluding the disease under study). A condition present at baseline that worsens after initiation of study treatment will be captured as an AE; the onset date will be the date the event worsened. The AE should be recorded in standard medical terminology when possible.

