9. OBJECTIVES

9.1. Primary Objective

The primary objective of this study is to assess long-term safety of EN3835 0.84 mg at scheduled intervals over 1 year (12 months) or more in all subjects with EFP who elect to enroll in this open-label trial regardless of their decision to receive treatment (re-treatment or re-dosing) of open-label EN3835 or opt to receive no treatment.

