17.5.1. Efficacy Analysis

The composite endpoints for cellulite severity are the proportions of composite responders defined as subjects with an improvement in severity from baseline of at least 2 (or 1) levels of severity in the CR-PCSS and an improvement in severity from baseline of at least 2 (or 1) levels of severity in the PR-PCSS.

These endpoints, will be summarized by treated quadrant and overall (buttocks and thighs) and by study day using appropriate descriptive statistics.

Other endpoints for treated quadrants include:

- Proportion at each level of improvement in the PR-PCSS:
 - Proportion of patient responders defined as subjects with an improvement in severity from baseline of at least 2 levels of severity in the PR-PCSS
 - Proportion of patient responders defined as subjects with an improvement in severity from baseline of at least 1 level of severity in the PR-PCSS
- Proportion at each level of improvement in the CR-PCSS:
 - Proportion of Investigator responders defined as subjects with an improvement in severity from baseline of at least 2 levels of severity in the CR-PCSS (Investigator rated)
 - Proportion of Investigator responders defined as subjects with an improvement in severity from baseline of at least 1 level of severity in the CR-PCSS (Investigator rated)

- Proportion of responders at each level of the I-GAIS:
 - Proportion of Investigator global responders defined as subjects with a response of 1 (improved) or better in the Investigator GAIS assessment
- Proportion of responders at each level of the S-GAIS:
 - Proportion of subject global responders defined as subjects with a response of 1 (improved) or better in the subject GAIS assessment
- Proportion of responders at each level of the subject satisfaction with cellulite treatment
- Change in the Hexsel CSS total score from screening visit

All endpoints will be summarized by treated region (buttock or thigh) and overall and by study day using appropriate descriptive statistics.

Observational endpoints include:

- Proportions of composite responders defined as subjects with an improvement in severity from baseline of at least 2 (or 1) levels of severity in the CR-PCSS and an improvement in severity from baseline of at least 2 (or 1) levels of severity in the PR-PCSS.
- Proportion at each level of improvement in the PR-PCSS:
 - Proportion of patient responders defined as subjects with an improvement in severity from baseline of at least 2 levels of severity in the PR-PCSS

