17.6. Safety Analyses

The following variables are safety endpoints.

- AEs: Mapped to preferred term using the Medical Dictionary for Regulatory Activities (MedDRA)
- Injection site reactions/local tolerability in selected quadrant (through subject and Investigator reporting)
- Vital signs
- Laboratory testing

AEs will be summarized by treatment group. AE duration will be summarized using descriptive statistics by treatment group.

Descriptive statistics will be presented for each clinical laboratory test for the actual and change from screening at each visit by treatment group and vital signs for the actual and change from Day 1 pre-injection for each injection day at each visit by treatment group.

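### Section 14.1.1 contradicts itself on whether worsened cellulite in a treated quadrant is an adverse event, and section 17.6 does not tabulate worsening as a safety outcome

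*Combined protocol and SAP*

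**What the plan says.** Section 9.1 sets the primary objective: to "assess long-term safety of EN3835 0.84 mg at scheduled intervals over 1 year (12 months) or more".

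**AE rules.** Section 14.1.1 opens with a broad definition, covering "any unfavorable or unintended change in body structure (signs") and "worsening of a pre-existing condition associated temporally with the use of the study medication". Later it gives examples of what must be recorded, ending with "progression of disease states (excluding the disease under study"). The sentence after that reads "A condition present at baseline that worsens after initiation of study treatment will be captured as an AE". Section 14.5.1 collects AEs until 30 days after the last dose, while Tables 2, 3 and 4 mark AEs as monitored for the whole study.

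**Scales.** Section 17.5.1 asks for "Proportion at each level of improvement in the CR-PCSS", defined as at least 2 and at least 1 levels better, and the same for the PR-PCSS. I-GAIS, S-GAIS and satisfaction are tabulated at each level. Hexsel is reported as change in the total score. One of its five items is "D) laxity, flaccidity or sagging of skin" (section 13.1.1.6). The observational endpoints in 17.5.1 are the composite, the two PCSS scales and the Hexsel total; GAIS is not listed.

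**Safety endpoints.** Section 17.6 lists AEs, vital signs, laboratory testing and "Injection site reactions/local tolerability in selected quadrant (through subject and Investigator reporting").

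**The concern.** It is reasonable to leave the disease under study out of AE recording if its worsening is counted somewhere else. Here the exclusion is contradicted by the sentence beside it, and no other table is built to count worsening.

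The harm is plausible on the protocol's own account. Section 8.3 says the drug lyses collagen in the dermal septa, and section 8.1 says those septa stabilise the subcutis. Section 8.2 names uneven contour and puckering among the side effects of other cellulite treatments. The protocol also foresees quadrants scoring worse than baseline, because sections 10.1 and 17.2 allow re-treatment at or above baseline severity.

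At stake is whether the report can say how often a treated quadrant ended worse or more lax than it started. As written, the AE count would depend partly on how each of the 15 sites reads section 14.1.1.

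**Working it through.** The plan gives no figure to reproduce. The check sets passages side by side and does arithmetic on the scales and the time window.

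**1. The two sentences in 14.1.1.** Take a treated quadrant rated 3 before injection and 4 at Day 180. Under the first sentence it is progression of the disease under study and is not recorded. Under the second it is a baseline condition that worsened and is recorded, with onset at the date of worsening. Neither sentence refers to the other. New laxity is a structural sign under the general definition, but it is also a Hexsel item, so a site could class it as the disease under study. The section does not say which applies.

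**2. PCSS (rated 0 to 4).** Treatment requires a baseline of 3 or 4. Room to worsen is 4 − 3 = 1 level from 3, and 4 − 4 = 0 levels from 4. A worsening rate therefore needs quadrants rated 3 on that scale as its denominator. In the improvement tables, an unchanged quadrant and one a level worse are both non-responders. Durability failure (17.5.2) is return to baseline among responders. It does not separate worse than baseline, and it never counts a non-responder who worsened.

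**3. Hexsel.** Five items scored 0 to 3 give 5 × 3 = 15, as stated; entry at 13 or below leaves at least 15 − 13 = 2 points of room. Masking is possible within the entry limit:

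| Item | A | B | C | D | E | Total |
|---|---|---|---|---|---|---|
| Baseline | 3 | 3 | 3 | 0 | 3 | 12 |
| Follow-up | 2 | 2 | 2 | 3 | 3 | 12 |
| Change | −1 | −1 | −1 | +3 | 0 | 0 |

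Laxity moves from none to severe and the reported change is 0.

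**4. GAIS (+3 to −3).** Three of the 7 levels mean worse, and all are tabulated for quadrants treated in this study, as efficacy. Observation-only subjects are also rated at Day 360, but GAIS is not in the observational list.

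**5. When each scale is rated (Tables 2 to 4).**
- PCSS: Screening B, Days 22, 43, 71, 90, 180, 270 and 360, then Days 450 to 720 for the long-term durability subset.
- Hexsel: Screening B, Day 71 and Day 360, then Days 450 to 720 for that subset.
- GAIS: Day 71 and Day 360.

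**6. AE window.** With a nominal last dose on Day 43, the window in 14.5.1 closes on Day 43 + 30 = 73. That leaves 360 − 73 = 287 days of scheduled follow-up outside it, which the schedule tables treat as monitored.

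**The case against.** The strongest reply is that 14.1.1 is ambiguous rather than prohibitive. The exclusion is a parenthesis in an illustrative list and speaks of progression, not of a change caused by the drug. The general definition, the TEAE definition (which includes worsening during treatment) and the next sentence all point towards recording. Local tolerability in the quadrant is a listed safety endpoint, reported by subject and investigator. Section 14.6.1 on events of special interest is redacted and may deal with local effects. All of this stands. It answers a reading that some might take from the exclusion: that a worsened quadrant will go uncounted and the AE tables will show zero. That would require every site to apply the exclusion, and the text does not oblige them to.

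A reader might also infer that every cellulite scale is reported only as improvement. That is true of the two PCSS scales alone. GAIS and satisfaction are shown at every level, and the Hexsel total is a signed change with minimum and maximum (synopsis, statistical methods), so a large rise in the total would be visible.

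The reply does not remove the conflict between the two sentences. The content of local tolerability is undefined, and nothing visible in 17.6 is defined as worse severity or more laxity. Nothing here rests on the redacted section.

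A further objection is that calling every 1-level shift an AE in an uncontrolled study would record rating noise. That is fair, and the fix does not ask for it.

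**Conclusion.** The point holds as two linked faults. Section 14.1.1 gives opposite instructions on cellulite worse than baseline in a treated quadrant. Worsening is also not tabulated as a safety outcome: it is merged into PCSS non-response, can net out within the Hexsel total, or sits among the efficacy summaries as GAIS. Capture is unreliable rather than absent.

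The documents give no rate of worsening, so no count of missed events can be defended. What can be sized is structural: a laxity rise of up to 3 points can be hidden at a net Hexsel change of 0, and 287 nominal days to Day 360 fall outside one of the two stated AE windows. The 287 days assume dosing on Day 43 exactly. The conclusion rests on section 17 as supplied; a separate analysis plan that tabulates worsening would settle the second fault but not the first. This is an inexpensive improvement worth making, not a flaw that invalidates the study.

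**What to change.** 1. **Section 14.1.1:** reconcile the two sentences so that one rule covers cellulite worse than baseline in an EN3835-treated quadrant, and state whether new or increased laxity is an AE.
2. **Section 14.5.1:** reconcile the 30-day window with Tables 2 to 4. Otherwise late worsening can be missed even where it counts as an AE.
3. **Section 17.6:** add one descriptive table, number and percentage of treated quadrants, at the visits where each scale is actually rated:
   - PR-PCSS and CR-PCSS separately: at least 1 level above baseline, among quadrants rated 3 on that scale at baseline.
   - Hexsel item D: increase of at least 1, among quadrants with baseline D below 3.
   - I-GAIS or S-GAIS: −1 or lower, including observation-only subjects.

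If the sponsor keeps the exclusion in 14.1.1, this table becomes the only systematic safety count of worsening.

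The cost is a short text change in two sections and one table. No new visit or instrument is needed, assuming the Hexsel item scores are kept in the database as well as the total. The downside is that some worsenings from natural fluctuation will be listed, which a footnote can say.

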14.1.2. Serious Adverse Event

A serious adverse event (SAE) is defined as an AE that:

- Results in death
- Is immediately life-threatening (there is an immediate risk of death from the AE as it occurred; this does not include an AE that had it occurred in a more serious form may have caused death)
- Results in or prolongs an inpatient hospitalization (Note: a hospitalization for elective or pre-planned surgery, procedure, or drug therapy does not constitute an SAE)

- Results in permanent or substantial disability (permanent or substantial disruption of one's ability to conduct normal life functions)
- Is a congenital anomaly/birth defect (in offspring of a subject using the study medication regardless of time to diagnosis)
- Is considered an important medical event

Important medical events are defined as events that, based upon appropriate medical judgment, may jeopardize the subject and may require medical or surgical intervention to prevent one of the other serious outcomes. Examples of important medical events include allergic bronchospasm requiring intensive treatment in an emergency room or at home, blood dyscrasias or convulsions that do not result in inpatient hospitalization, or the development of drug dependency or drug abuse.

14.2. Monitoring Adverse Events

At each visit, subjects will be queried regarding any AEs that have occurred since the last visit. Subjects will be asked to volunteer information concerning AEs with a non-leading question such as, "How do you feel?" Study site personnel will then record all pertinent information in the source documents and the eCRF. The study drug compliance record should also be reviewed to detect potential overdoses (intentional/unintentional).

14.3. Relationship to Study Drug

The degree of "relatedness" of the AE to the study medication must be described using the following scale:

- **Not related** indicates that the AE is definitely not related to the study medication.
- **Unlikely related** indicates that there are other, more likely causes and study medication is not suspected as a cause.
- **Possibly related** indicates that a direct cause and effect relationship between study medication and the AE has not been demonstrated, but there is evidence to suggest there is a reasonable possibility that the event was caused by the study medication.
- **Probably related** indicates that there is evidence suggesting a direct cause and effect relationship between the AE and the study medication.

It is the Sponsor's policy to consider "Probably related" and "Possibly related" causality assessments as positive causality. "Not related" and "Unlikely related" causality assessments are considered as negative causality.

Assessments will be recorded on the eCRF and must indicate clearly the relationship being assessed. For example, an AE that appears during a placebo run-in phase would be assessed with respect to the placebo treatment received and/or study procedures conducted during this phase. If the AE continued into an active treatment phase, the relationship would be assessed for the active treatment phase only if the AE worsened.

14.4. Intensity Assessment

The intensity (or severity) of AEs is characterized as mild, moderate, or severe:

- **Mild** AEs are usually transient, requiring no special treatment, and do not interfere with the subject's daily activities.
- **Moderate** AEs introduce a low level of inconvenience or concern to the subject and may interfere with daily activities, but are usually ameliorated by simple therapeutic measures.
- **Severe** AEs interrupt a subject's usual daily activity and typically require systemic drug therapy or other treatment.

When the intensity category of an AE changes, the greatest intensity during that continuous episode should be recorded.

14.5. Reporting Adverse Events and Serious Adverse Events

14.5.1. Reporting Adverse Events

Throughout the study, AEs will be documented on the source document and on the appropriate page of the eCRF whether or not considered treatment-related. This includes any new signs, symptoms, injury or illness, including increased severity of previously existing signs, symptoms, injury, or illness. Conditions existing prior to screening will be recorded as part of the subject's medical history. The Investigator is responsible for assessing the relationship of AEs to the study medication; relationship will be classified as not related, unlikely related, possibly related, or probably related.

All AEs will be collected by the Investigator from the time of signing the informed consent through 30 days after the last dose of study medication; this includes any AEs that are ongoing at the time of completion/termination of the study. All ongoing AEs must be followed until resolution or for 30 days after the subject's last study visit, whichever comes first.

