5. SCHEDULE OF EVENTS

NOTE: Observation visits ([Table 2](#)) in the open-label extension study begin after completion of double-blind study (Day 71). Treatment sessions ([Table 3](#)), if elected, will begin after study drug blind is broken in study EN3835-201 while observation visits continue concurrently.

Table 2: Observation Assessments

Procedures	Screening A ^a (≥Day 71 Visit of Double-blind Study)	Visit 1 Day 90 ^b (±7 days)	Visit 2 Day 180 ^b (±7 days)	Visit 3 Day 270 ^b (±7 days)	Visit 4 End of Study/ Early Termination Day 360 ^{b,f} (±7 days)
Informed Consent	X				
Inclusion/Exclusion	X				
Digital photography		X ^c	X ^c	X ^c	X ^c
Prior/Concomitant Medications/Procedures	X	X	X	X	X
Body weight		X	X	X	X
Vital signs		X	X	X	X
Collection of samples:					
• Clinical laboratory					X
• Anti-AUX-I/anti-AUX-II antibody level					X
Subject cellulite assessments:					
• Patient Reported Photounumeric Cellulite Severity Scale (PR-PCSS)		X ^{d,e}	X ^{d,e}	X ^{d,e}	X ^{d,e}
• Subject Global Aesthetic Improvement (S-GAIS)					X ^{d,e}
• Subject satisfaction with cellulite treatment assessment					X ^{d,e}
Investigator cellulite assessments:					
• Clinician Reported Photounumeric Cellulite Severity Scale (CR-PCSS)		X ^e	X ^e	X ^e	X ^e
• Hexsel Cellulite Severity Scale (CSS)					X ^e
• Investigator Global Aesthetic Improvement (I-GAIS)					X ^e
Injection site reactions/local tolerability in assigned quadrant from EN3835-201 study		X	X	X	X
Adverse events		Monitored Throughout Study			

^a Informed consent for open-label observation assessments and optional treatment election.

^b Four (4) visits at 3-month periods begin 90 days after Day 1 of the double-blind study (EN3835-201) (ie, within 20 days ± 4 days of completion of double-blind study).

^c Only the treated quadrant(s) is photographed. For subjects participating in observation-only visits, the quadrant treated in the double-blind study (EN3835-201) is photographed; for subjects with open-label treatment (treated with EN3835 in study EN3835-202), the treated quadrant is photographed.

^d Assessment made via viewing digital image photograph.

^e Assessment of treated quadrant(s) only.

^f For subjects treated with active EN3835 in the double-blind study and having a different quadrant treated in the open-label study, refer to Table 4 for continued assessments of the double-blind treated quadrant for durability beyond Day 360.

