14.5.2. Reporting Serious Adverse Events

Any SAE, including death resulting from any cause, which occurs to any subject participating in this study must be reported via email or fax by the Investigator using the Endo Clinical Trial Report Form for SAEs within 24 hours of first becoming aware of the SAE. SAEs will be collected by the Investigator from the time of signing the informed consent through 30 days after the last dose of study medication. SAEs that occur within 30 days, following cessation of the study treatment, or within 30 days, following premature discontinuation from the study for any reason, must also be reported within the same timeframe. Any SAE that is considered by the Investigator to be related to the study medication must be reported regardless of the amount of time since the last dose received. Follow-up information collected for any initial report of an SAE must also be reported to the Sponsor within 24 hours of receipt by the Investigator.

All SAEs will be followed until resolution, stabilization of condition, or until follow-up is no longer possible.

In the event discussion is necessary regarding treatment of a subject, call the Medical Monitor (see contact information in section 3).

All SAEs should be sent via the email address, or faxed to the fax number, provided in section 3.

The Sponsor will determine whether the SAE must be reported within 7 or 15 days to regulatory authorities in compliance with local and regional law. If so, the Sponsor (or the Sponsor's representative) will report the event to the appropriate regulatory authorities. The Investigator will report SAEs to the institutional review board (IRB) per their IRB policy.

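### The protocol gives two contradictory end points for AE and SAE collection (30 days after the last dose, or throughout the study), although its primary objective is safety over 12 months or more

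*Combined protocol and SAP*

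**What the plan says.** The references are to the current protocol (Amendment 4).

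- **Objective.** Section 9.1 sets out to "assess long-term safety of EN3835 0.84 mg at scheduled intervals over 1 year (12 months) or more in all subjects with EFP", whether or not they take open-label treatment.
- **The 30-day rule.** Section 14.5.1 has all AEs "collected by the Investigator from the time of signing the informed consent through 30 days after the last dose of study medication". Section 14.5.2 repeats it: "SAEs will be collected by the Investigator from the time of signing the informed consent through 30 days after the last dose of study medication".
- **The throughout-study rule.** Section 14.5.1 itself opens: "Throughout the study, AEs will be documented on the source document and on the appropriate page of the eCRF". Section 14.2 says: "At each visit, subjects will be queried regarding any AEs that have occurred since the last visit", with the answers entered in the eCRF. The AE rows of Table 2 (Days 90 to 360) and Table 4 (Days 450 to 720) both read "Monitored Throughout Study".
- **SAEs.** Section 14.5.2 opens by requiring a report of any SAE, from any cause, in any participating subject. After the 30-day sentence it adds SAEs within 30 days of stopping treatment or of leaving the study early. It also says that an SAE judged related "must be reported regardless of the amount of time since the last dose received".
- **Ongoing AEs.** Section 14.5.1 follows these to resolution or to 30 days after the last study visit, so a second clock appears in the same paragraph.

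**The concern.** The 30-day sentence is the only AE collection text that names both a start and an end. It is stated once for AEs and again for SAEs, so a site could reasonably take it as the operative rule. Amendment 4 lengthened the objective in section 9.1 and added the Day 450 to 720 schedule, but left the collection wording in section 14.5 as it stood in Amendment 3.

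If sites follow different sentences, they collect different data. Section 17.6.4 tabulates numbers and percentages of subjects with events. Such a table cannot tell a subject with no event at month 9 from a subject whose events were no longer being recorded. The error runs one way, towards too few late AEs. Its size would also differ between the cohorts of section 17.2, because time since the last dose differs between them.

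**Working it through.** The documents give no figure for the length of AE collection, so this is day arithmetic, with Day 1 as the first injection.

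**Inputs.** Sessions fall on Days 1, 22 and 43, with ±3 days on the second and third (Table 3). Entry to this study is at or after Day 71 of EN3835-201 (Table 2). Former placebo subjects may have two open-label courses (section 12.1.4). Screening B for the second course may take place on Day 71 of the first (section 10.1) and precedes dosing by 1 to 14 days (Table 3).

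**Check on day counting.** Section 10.1 requires at least 28 days after the end of the first course and gives Day 71 as its example: 43 + 28 = 71. This agrees.

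**Formula.** End of the literal window = day of last dose + 30.

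| Subject | Last dose | Window ends | Share of 360 days |
|---|---|---|---|
| One full course | Day 43 | 43 + 30 = Day 73 | 73/360 = 20.3% |
| One full course, visit window | Day 40 to 46 | Day 70 to 76 | 19.4% to 21.1% |
| Session 1 only | Day 1 | Day 31 | 8.6% |
| Sessions 1 and 2 only | Day 22 | Day 52 | 14.4% |
| Two open-label courses, second Day 1 on Day 72 to 85 | 72 + 42 = 114 to 85 + 42 = 127 | Day 144 to 157 | 40.0% to 43.6% |

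For an observation-only subject whose last dose was on Day 43 of EN3835-201, the window ends on Day 73 of that study. Entry is on Day 71 or later, so at most 73 − 71 = 2 days are covered, out of 360 − 71 = 289 days from Day 71 to Day 360. A later entrant has none.

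**Against the visit schedule.** After one full course, every visit in Tables 2 and 4 (Days 90, 180, 270, 360, 450, 540, 630 and 720) falls outside the literal window. After two courses, the Day 180, 270 and 360 visits counted from first exposure still do.

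**What other safety data exist after the window.** Table 2 schedules vital signs at all four visits, local tolerability for the EN3835-201 quadrant at all four, and laboratory and antibody samples at Day 360 only. Table 4 schedules none of these, so in the Day 450 to 720 extension AEs are the only scheduled safety assessment.

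**The case against.** The strongest reply is that the intent is plain. The opening of section 14.5.1, section 14.2, the AE rows of both tables and the objective all point to collection throughout the study, and section 14.1.1 requires all AEs to be recorded without giving an end date. A site that keeps recording is following most of the protocol. Because treatment may be elected after entry, a site also cannot know at entry that an observation-only subject has already had her last dose. All of this stands. It shows that the defect is a contradiction and which way to resolve it, but it does not remove a sentence written into two sections.

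A reader might infer more: that AE collection simply stops at Day 73 and the primary objective rests on the first 73 days. The documents do not support that, for four reasons.

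- The throughout-study rule is equally part of the text.
- SAE reporting does not simply stop. Related SAEs have no time limit, and the opening of section 14.5.2 covers unrelated SAEs during participation, so only the unrelated ones are caught in the contradiction.
- Vital signs, local tolerability, laboratory and antibody data run to Day 360.
- Day 73 applies to one full course, not to everyone.

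Nor should Day 73 be set against 720 days for treated subjects. Table 4 counts from Day 1 of EN3835-201, whereas an open-label course has its own Day 1. A subject whose open-label Day 1 falls on Day 180 of EN3835-201 would have a window ending at 180 + 42 + 30 = Day 252 on that clock.

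**Conclusion.** The concern holds as an internal contradiction that touches the primary objective, and the text is wrong as written. Under the 30-day sentence, recording of new non-serious AEs would end at about Day 73 (70 to 76) after one full course, at about Day 144 to 157 from first exposure after two open-label courses, and 0 to 2 days after entry for observation-only subjects. Under the other rule it runs to Day 360, or to Day 720 in the long-term durability extension. The documents do not show which rule sites followed, so the shortfall in late AEs is possible but not established.

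Assumptions: nominal visit days except where the ±3-day window is shown; a second course that follows Screening B on Day 71 (a later start moves the end later); and, for observation-only subjects, that the last dose means the Day 43 dose in EN3835-201. The protocol does not define the last dose for them, so their end date is strictly undefined.

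**What to change.** In sections 14.5.1 and 14.5.2, replace the end of the collection window with: *through the subject's last study visit under Table 2, 3 or 4, or 30 days after the last dose, whichever is later*. State that this applies to treated, observation-only and long-term durability subjects alike. Keep the provision that related SAEs are reportable without time limit. Both sections then agree with section 9.1, section 14.2 and the AE rows of Tables 2 and 4, and observation-only subjects no longer depend on an undefined last dose.

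The cost is two sentences of protocol text and a little more eCRF entry. The visits, and the AE query at each of them, are already scheduled.
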